### 288 D2 Clinical Data to Date

Gabapentin is an antiepileptic medication now used as first-line therapy for diabetic neuropathy and herpetic neuralgia. Gabapentin works by binding to voltage-gated calcium channels (VGCCs), which play an important role in neuronal synaptic transmission. More specifically, gabapentin binds to  $\alpha_2\delta$  isoforms which have been associated with neuropathic pain.

294

The medication has also proven effective in treated chronic pain from Burning Mouth Syndrome (BMS) since gabapentin is highly lipophilic and can enter the central nervous system (CNS). For these reasons, gabapentin is thought to have the potential to improve post-COVID-19 olfactory dysfunction caused by neuronal damage. Gabapentin can penetrate the blood-brain barrier and enter the CNS where it can aid in neuron regeneration.

### 301 D3 Dose Rationale and Risk/Benefits

Gabapentin dosing for this study mirrors dosing for the prior study "Relief of Idiopathic
 Subjective Tinnitus" (IRB #02-0717)

- Following randomization, participants in the gabapentin arm will take gradually titrated dosages in order to achieve a dose of 3600mg/d or highest tolerable dose. The titration schedule will span a maximum 4 weeks to reach 3600mg/d.
- 307 Week 1, 900 mg/d
- 308 Week 2, 1800 mg/d
- 309 Week 3, 2700 mg/d
- 310 Week 4, 3600 mg/d
- 311

312	Gabapentin (300 mg per capsule) and placebo will be supplied to patients in
313	identical opaque capsules in blinded fashion. The medications will be distributed in 4
314	separate vials representing each of the four weeks of the Titration Period. All
315	participants will be provided an equal number of capsules and instructed to follow a TID
316	(i.e., 3 times per day) dosing schedule. All participants' dosages will be titrated to a
317	maximum dose of 3600 mg/d, regardless of any possible beneficial effect achieved at
318	lower dosages. If intolerable adverse reactions occur, the dosage will be decreased to
319	previous tolerable dose (e.g. if 2700mg/d is intolerable, dosage will be decreased to 1800
320	mg/d). If, during the first week, 900 mg/d is intolerable, dosing will be decreased by 300
321	mg/d per day until tolerable (i.e., 600 mg/d, 300mg/d) or until they are no longer taking
322	the medication. The dose established during the Titration Period will be maintained
323	throughout the Fixed-Dose period. Participants receiving the matching placebo capsules
324	will be provided similar instructions for titration and de-escalation, should side effects
325	develop.
326	-

The potential benefit to the participant is improvement of their olfactory dysfunction
using this therapy. The potential benefit to the society is the use of the pilot study results
to initiate a larger trial to further evaluate the efficacy of gabapentin in the treatment of
post-COVID-19 olfactory dysfunction.

331

The potential risk to participants during the study is an adverse event associated with the medication use. Abrupt cessation of gabapentin may alter the seizure threshold; for this reason, participants will be provided with a taper schedule specific to the gabapentin dose at time of completion of the Fixed Dose period. Gabapentin has a slight risk of dependence in patients with previous history of alcohol, cocaine, or opioid abuse so these individuals will be excluded from the study.

338

339 E Study Design

340

### 341 E1 Overview or Design Summary

This study will be a double-blinded, placebo-controlled, randomized pilot clinical trial to evaluate the efficacy of gabapentin to improve post-COVID-19 olfactory dysfunction.

- 344 This study will also describe adverse effects related to oral gabapentin use.
- 345

This study will be conducted via virtual research guidelines and procedures. We will not require in-person patient participation or evaluation. Following initial evaluation to ensure potential participants meet all inclusion criteria and none of the exclusion criteria,

the research study will be explained in full via Zoom call, phone call if necessary.

350 Participants will then be randomized in a 1:1 allocation via permuted-block sequencing

into the oral gabapentin group or the placebo group. All assessments will be conductedthrough a HIPAA-compliant online survey form. Baseline assessments will help us

determine subjective and objective rates of olfactory dysfunction. Assessments will be

354 conducted again after the 8-week Fixed-Dose period and 4 weeks after completing taper.

355 356	The primary objective of this study is to assess the efficacy of oral gabapentin in improving olfactory dysfunction secondary to COVID-19.
357	E2 Subject Selection and Withdrawal
358	
359	2.a Inclusion Criteria
360	Participants will be recruited based on the following inclusion criteria:
361	- Men and women between the ages of 18 and 65 years
362	- Residing within the states of Missouri or Illinois
363	- Clinically diagnosed or subjective olfactory dysfunction (anosmia, hyposmia,
364	or parosmia) of at least 3 months duration associated with COVID-19
365	infection

- 366- initial UPSIT score consistent with diminished olfactory function (score  $\geq 6$ 367and  $\leq 33$  in men and score  $\geq 6$  and  $\leq 34$  in women).
- Willing to respond daily to study surveys, preferably through smartphone with
   unlimited texting plan.
- In possession of all 7 household items associated with *NASAL-7*: soap, burnt
  candle, peanut butter, herb, garlic, lemon, and coffee

373 2.a Exclusion Criteria

Individuals will not be allowed to participate in this study if they meet one or more of thefollowing exclusion criteria:

- Clinically diagnosed olfactory dysfunction secondary to non-COVID-19 viral
   infection, genetic abnormalities or congenital dysfunction, trauma, nasal
   polyps, neurodegenerative disorders
- 379
  380
  Current use of: azelastine, bromperidol, orophenadrine, oxomemazine, kratom, paraldehyde, or thalidomide
- 381 History of addiction to alcohol, cocaine, or opioids
- 382 Impaired renal function, myasthenia gravis, or myoclonus
- 383 Severe allergy to peanuts
  384 Pregnancy or attempting p
  - Pregnancy or attempting pregnancy during study participation
- Inability to participate in virtual trial due to lack of access to the; inability to
   comprehend or use English language
- 387 Availability less than 18 weeks from time of enrollment
- 388 Residency in states other than Missouri or Illinois.
- 389 **2.b** Ethical Considerations
- This study relies on participation of human subjects. Informed consent will be obtained from each participant to ensure their safety, minimize risk, and ensure full confidentiality. All assessments will be conducted virtually via HIPAA-compliant online surveys at baseline and then throughout the study course. Selection of participants for the study will consider the variability in response to COVID-19 as well as response to gabapentin by ensuring the two groups are matched 1:1 by permuted block randomization. Gabapentin has a slight risk of dependence in individuals with previous

history of alcohol, cocaine, or opioid abuse so these patients will be excluded from the

study.The study team will be available at all times for participants during the full course
 of the trial.

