### 420 **2.e Risks and Benefits**

The potential benefit to the participant is improvement of their olfactory dysfunction
using this therapy. The potential benefit to the society is the use of the pilot study results
to initiate a larger trial to further evaluate the efficacy of gabapentin in the treatment of
post-COVID-19 olfactory dysfunction.

425

The potential risk to participants during the study is an adverse event associated with the medication use. Abrupt cessation of gabapentin may alter the seizure threshold; for this reason, participants will be provided with a taper schedule specific to the gabapentin dose

429 at time of cessation. Gabapentin has a slight risk of dependence in individuals with

- 430 previous history of alcohol, cocaine, or opioid abuse so these individuals will be excluded
- 431 from the study. 17
- 432
- 433 The consent process informs a volunteer about the study, indicates that participation is
- 434 voluntary, and that he/she has the right to stop at any time. Risks are listed in the
- 435 informed consent form and described orally during the consent process.
- 436

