### 587 Gabapentin (300 mg pill) Titration Schedule

588

586

589 If at any point during the Titration Period, the participant wishes to discontinue 590 the medication for any reason, they will be instructed to follow the taper down schedule 591 (see below) in order to safely stop the medication. The participant will be informed that 592 any abrupt stoppage of gabapentin could cause serious adverse effects.

Participants will be contacted by telephone or video call by the Research Assistant
(RA) at the end of Titration period. The purpose of this call will be to query the
participants about adverse effects. Participants will be provided with a paper calendar
and asked to maintain diaries of olfactory and taste symptoms and adverse effects
possibly related to the intervention.

598 Participants will not complete any forms at the completion of Titration period.599 Instead, they will proceed directly to Fixed-Dose Period.

### 600 601

Fixed-Dose Period: duration 8 weeks

602During the Fixed-Dose period, participant's dose will remain at their maximum tolerated603dosage established during the Titration phase. The study drug will be distributed in eight604separate vials representing the eight weeks of the Fixed-Dose period. The RA will605contact the participants at the end of Week 4 to administer the blind assessment using606REDCap (survey titled: "Blind Assessment"). Participants will complete the following607forms after completing the Fixed-Dose Period (survey titled: "FixedDoseSurvey"):

- 608
- 609 1.) Clinical Global Impression of Severity Scale (CGI-S).

610 2.) Clinical Global Impression of Improvement Scale (CGI-I)

- 611 3.) University of Pennsylvania Smell Identification Test (UPSIT)
- 612 4.) Olfactory Dysfunction Outcomes Rating (ODOR)
- 613 5.) *NASAL-7*
- 6.) *Clinical Global Impression-Severity Scale for Parosmics (CGI-P)*
- 615 7.) Adverse Event assessment
- 616 8.) Compliance
- 617

618 *Adverse events*. Any unintentional or unfavorable clinical sign or symptom, any new

619 illness or disease or the deterioration of existing disease or illness, or any clinically

620 significant deterioration in any laboratory assessments or clinical tests while participating

621 in this study will be captured. The study coordinator will contact participants virtually to

622 answer questions and assess adverse effects after Titration period, Fixed-Dose period,

- 623 and 4 weeks after Taper.
- 624

- 625 Taper Down: maximum duration 2 weeks

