### The specific monitoring plan for this study is based on the potential risk of participation

and size and complexity of the planned investigation. Based on these considerations, this

- study will have a monitoring committee comprised of [name], [name], and
- 654 [name], the study biostatistician. All reports of a Serious Adverse Event (SAE) or

- 655 an Unexpected Adverse Event (UAE) will be investigated by the monitoring team and 656 reported to Washington University HRPO according to the reporting requirements. 657 658 Participants who experience serious adverse effects with gabapentin therapy will be 659 removed from the study. Participants with serious adverse effects will be instructed to 660 call 911, seek immediate medical care and discontinue all further gabapentin treatment. If 661 tolerated, all participants will complete the Titration period ( $\leq 4$  weeks), Fixed-Dose 662 period (8 weeks), and Taper-Down period (2 weeks) for maximum 14 weeks of active participation. In addition, there will be a 4-week, post-Taper completion follow-up for 663 664 maximum total of 18-week trial duration.
- 665 **3.a Medical Monitoring**
- 666

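### The protocol names a seizure-threshold risk on abrupt cessation, but no eligibility criterion addresses seizure history, and the taper meant to contain the risk is not assured

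*Combined protocol and SAP*

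**What the plan says.** **The risk.** D3 (Dose Rationale and Risk/Benefits) and E2 2.e (Risks and Benefits) both state that "Abrupt cessation of gabapentin may alter the seizure threshold". The Titration Period text in F2 requires participants to be told that "any abrupt stoppage of gabapentin could cause serious adverse effects".

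**The mitigation.** Section 2.e says that for this "reason, participants will be provided with a taper schedule specific to the gabapentin dose" at cessation. D3 says the same for the end of the Fixed-Dose period. Section 2.f provides a taper on early withdrawal, and F2 provides one for a participant who stops during titration. The Taper Down table in F2 gives the schedules.

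**Eligibility.** The items in E2 2.a that could bear on this are:

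- the medical conditions: "Impaired renal function, myasthenia gravis, or myoclonus";
- the barred drugs: "Current use of: azelastine, bromperidol, orophenadrine, oxomemazine, kratom, paraldehyde, or thalidomide";
- the substance history: "History of addiction to alcohol, cocaine, or opioids";
- an item on non-COVID causes of the olfactory loss, which ends with "polyps, neurodegenerative disorders".

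None concerns seizures or epilepsy. F1 describes an online questionnaire that checks the listed criteria.

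**Stopping.** F3 3.a tells participants with serious adverse effects to "call 911, seek immediate medical care and discontinue all further gabapentin treatment".

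**The concern.** The protocol identifies a hazard of stopping the drug and treats it seriously enough to plan a taper in both arms and to warn participants. Yet nothing in the described screening would reveal whether a candidate has ever had a seizure, so nobody is prompted to judge whether this matters for that candidate. Screening and follow-up are remote, and E1 requires no in-person evaluation, so the omission is unlikely to be caught by a clinical visit.

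At stake is participant safety, and also the interpretation of adverse events. In a trial of this size, a single seizure in someone whose history was not recorded would be hard to attribute, either to the drug or to the earlier condition.

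**Working it through.** The plan gives no figure to reproduce. The check is a reading of the passages side by side, followed by a small calculation of scale.

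**Step 1: is there a criterion anywhere?**

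- E2 2.a: the printed line numbers of the exclusion list run from 376 to 388 without a gap, so no item appears to have been lost in extraction. There is no seizure or epilepsy entry.
- The seven barred drugs are not a general bar on antiepileptic drugs, so they do not remove people with epilepsy indirectly.
- Neurodegenerative disorders appear only as a cause of the olfactory dysfunction.
- E3 3.f restricts treatments for olfactory dysfunction only.
- No exclusion at the investigator's discretion is stated.
- F1 ties the screening survey to the listed criteria. The form itself is not in the text, so it might ask about seizures, but nothing says that it does.

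**Step 2: is the taper assured?**

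| Section | What it provides |
|---|---|
| D3, 2.e, 2.f, F2 | A taper at the end of treatment, on withdrawal, or on stopping in titration |
| F3 3.a | Discontinuation after serious adverse effects; no taper mentioned |
| 2.g | After a drug-related serious adverse event, a taper or a complete stop, by clinical judgement |
| F2 taper table | Columns for 3600, 2700, 1800 and 900 mg only |
| E3 3.b and F2 Titration Period | Step-down by 300 mg, for example from 2700 to 2400 mg/d |

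The last two rows do not fit together if the taper follows the dose at the time of stopping, as D3 and 2.e say: 2400 mg/d has no column. They fit better if it follows the maximum dose achieved, as 2.f and the Taper Down text say. The sections differ on which applies.

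**Step 3: scale.** Inputs:

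- N = 60 to be enrolled and randomised in balance (G1), with 1:1 allocation (E1), so n = 60/2 = 30 on gabapentin.
- Prevalence p of a seizure history among otherwise eligible people: not in the documents; assumed 0.5%, 1% or 2%.

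Chance that at least one gabapentin participant has such a history = 1 − (1 − p)^30. Expected number among 60 candidates = 60p.

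| Assumed p | 1 − (1 − p)^30 | 60p |
|---|---|---|
| 0.5% | 1 − 0.860 = 14% | 0.3 |
| 1% | 1 − 0.740 = 26% | 0.6 |
| 2% | 1 − 0.545 = 45% | 1.2 |

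E3 3.c speaks of 20 persons per group, which in G1 is the number evaluable after drop-out. With n = 20 the chances would be 1 − 0.905 = 10%, 1 − 0.818 = 18% and 1 − 0.668 = 33%. Exposure concerns everyone randomised to the drug, so 30 is the better denominator.

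**The case against.** The strongest reply is that the plan is coherent as it stands. Dependence is described as a risk of people with a substance history, so excluding them follows. The seizure-threshold risk is described for all participants, so a taper for all follows. This part stands: a reader might infer that the protocol contradicts itself by treating its two named risks differently, but the wording does not support that. The documents name no higher-risk group for seizures, and the greater vulnerability of people with a seizure history is a clinical inference.

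The safeguards also go beyond the taper schedule: taper capsules in both arms (E3 3.h, F2), check-ins every two weeks (3.e), and round-the-clock contact (F3, Medical Monitoring).

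Other stronger readings should also be resisted:

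- *That the protocol says stopping lowers the threshold or causes seizures.* It says only that the threshold may be altered, although the taper and the warning in F2 show that this is treated as a harm.
- *That the 33% drop-out in G1 means a third stop abruptly.* That figure sizes the evaluable sample, and 2.f gives withdrawing participants a taper.
- *That 14 weeks of drug are followed by withdrawal.* C1 and F3 3.a include the taper within the 14 weeks.
- *That the relevant chance is 26%, 45% or 70%.* Those values come from 1 − (1 − p)^60 and include the placebo arm, which has no gabapentin to stop.

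What the reply does not remove is that the sole measure aimed at this risk is a taper, that the protocol's own text permits stops without one, and that seizure history is not part of the described screening.

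**Conclusion.** The point holds as a gap between a named risk and the eligibility list, not as a contradiction. The protocol names the seizure-threshold risk twice, has no criterion on seizure history, and relies on a taper that its own stopping passages and taper table leave incomplete.

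Its size is modest and rests on an assumption: for a prevalence of 0.5% to 2%, there is a 14% to 45% chance that at least one of about 30 gabapentin participants has a seizure history. This is the chance of enrolling such a person on the drug, not the chance of an untapered stop or of a seizure; the documents give no basis for either. The verdict also assumes that the screening survey follows the listed criteria, as F1 says. It is worth correcting because the hazard is the protocol's own and the correction is small.

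**What to change.** Reconcile the eligibility list in 2.a and the screening survey in F1 with the risk named in D3 and 2.e, so that seizure history is asked at screening and its effect on eligibility is set by the investigators and stated, with the reason. Which clinical rule applies is for them to decide.

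In the same revision, reconcile the passages on stopping: the discontinuation instruction in F3 3.a, the complete stop allowed in 2.g, the warning in F2, and the taper table against the step-down doses in E3 3.b and F2. State also whether the taper follows the dose at stopping or the maximum dose achieved.

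The cost is one screening question, one line in 2.a and an edit to the stopping text. If the investigators chose to exclude people with a seizure history, the expected loss at the assumed prevalences is 0.3 to 1.2 of 60 candidates. The analysis would not change.

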#### 481 3.c Method for Assigning Subjects to Treatment Groups

482 The participants will be divided using permuted block randomization in a 1:1 allocation

- 483 between two arms: the oral gabapentin group and the oral lactose placebo group with 20
- 484 persons in each group.

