### 542 Gabapentin Study Flow Chart

549	
550	
551	
552	
553	
554	a. Federal guidelines require timely reporting (within 15 calendar days) of an
555	unanticipated or life-threatening event or death occurring within 30 days of
556	active study participation.
557	
558	
559	Titration Period: maximum duration 4 weeks
560	
561	Placebo. In this study, we plan to use an inert placebo and not an active drug
562	or non-active drug with side effects similar to gabapentin. Participants randomized to the
563	Placebo arm will participate in a 4-week Titration Period. Placebo will be supplied to
564	patients in opaque capsules in blinded fashion. The medications will be distributed in 4
565	separate vials representing each of the four weeks of the Titration Period. If intolerable
566	adverse reactions occur, the dosage will be decreased to prior tolerable dose.
567	Gabapentin. Participants randomized to the gabapentin arm will take
568	gradually titrated dosages of gabapentin as follows:
569	
570	Week 1, 900 mg/d (300 mg TID)
571	Week 2, 1800 mg/d (600 mg TID)
572	Week 3, 2700 mg/d (900 mg TID)
573	Week 4, 3600 mg/d (1200 mg TID)
574	
575	Gabapentin (300 mg per capsule) will be supplied to participants in opaque
576	capsules in blinded fashion identical to the supply of Placebo. The medications will be
577	distributed in 4 separate vials representing each of the four weeks of the Titration Period.
578	All participants' dosages will be titrated to a maximum dose of 3600 mg/d, regardless of
579	any effect achieved at lower dosages. If intolerable effects occur, dosage will be
580	decreased by 1 dose (300 mg) step (e. g. if 2700 mg/d is intolerable, dosage will be
581	decreased to 2400 mg/d). Further de-escalation will be determined by PI clinical
582	judgement to prior tolerable dose. Participants with intolerable effects may have a lower
583	maximum dose than 3600mg/d and may complete the Titration Period in less than 4
584	weeks. The dose established during the Titration Period will be maintained throughout
585	the Fixed-Dose period.

WEEK 1	WEEK 2	WEEK 3	WEEK 4
900 MG	1800 MG	2700 MG	3600 MG
1 MORNING 1 NOON 1 NIGHT (21 PILLS)	2 MORNING 2 NOON 2 NIGHT (42 PILLS)	3 MORNING 3 NOON 3 NIGHT (63 PILLS)	4 MORNING 4 NOON 4 NIGHT (84 PILLS)

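### No exclusion criterion covers known hypersensitivity to gabapentin or to a capsule ingredient, although eligibility is screened remotely and the capsules are sent by courier

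*Combined protocol and SAP*

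**What the plan says.** The exclusion list in section E2 covers other causes of smell loss, selected current medicines, past addiction, selected medical conditions, one allergy, pregnancy, access and language, availability and residency. The items closest to this point are:

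- Allergy: "Severe allergy to peanuts". The inclusion criteria explain it, because the household items needed for NASAL-7 include "candle, peanut butter, herb, garlic, lemon, and coffee".
- Medical conditions: "Impaired renal function, myasthenia gravis, or myoclonus".
- Medicines: "Current use of: azelastine, bromperidol, orophenadrine, oxomemazine, kratom, paraldehyde, or thalidomide". This concerns current use of seven named agents and does not mention gabapentin.

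On the products taken, section E3 3.c names the two arms as "the oral gabapentin group and the oral lactose placebo group". The titration table in section F2 reaches "4 MORNING 4 NOON 4 NIGHT (84 PILLS") in week 4, and that level is carried through the 8-week Fixed-Dose period if tolerated.

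On screening, section F1 uses an online questionnaire to check the listed criteria, followed by a mailed UPSIT and electronic consent. Section E1 states that no in-person evaluation is required. Sections 2.d, 3.g and 3.h have the study drug delivered by FedEx.

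**The concern.** The list guards against an allergen that participants only smell and is silent on what they swallow three times a day for up to 14 weeks. In a clinic-based trial, a history taken at the visit might catch a known drug reaction even without a written criterion. Here the written criteria are the main filter, and section 2.c draws applicants from registries, website postings and support groups as well as clinics. At stake is the avoidable exposure of a person already known to react to the study drug or to a capsule ingredient.

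**Working it through.** **1. Trace one applicant through the plan.** Take an adult who meets all inclusion criteria and has a documented hypersensitivity reaction to gabapentin.

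- Medicines item: not met, since gabapentin is not among the seven agents and only current use counts.
- Medical conditions item: not met.
- Allergy item: not met, since it names peanuts only.
- Section 3.f (prior therapy): people who tried earlier treatments for smell loss stay eligible, so previous exposure to gabapentin is no filter.
- Section F1: the questionnaire is described as checking the listed criteria, so this person passes as the criteria stand.

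The same trace holds for a person with milk allergy or known lactose intolerance who is assigned to the lactose placebo.

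**2. When do the other safeguards act?** Dose reduction (sections D3, 3.b and F2), two-weekly check-ins (3.e), adverse-event calls (F2) and round-the-clock contact (F3) all start once capsules are being taken. None prevents the first exposure.

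**3. Amount taken.** The plan's own weekly counts reproduce: 3 × 7 = 21, 6 × 7 = 42, 9 × 7 = 63 and 12 × 7 = 84 capsules. At the top level:

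- titration: 21 + 42 + 63 + 84 = 210
- fixed dose: 84 × 8 = 672
- taper: 3 × (9 + 6 + 3) = 54
- total: 936 capsules, with a peak of 12 a day

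**4. Chance of at least one affected participant.** Section G1 plans 60 participants randomised evenly, so 30 per arm. The frequency q of known gabapentin hypersensitivity among applicants is not given; assume 0.1% to 1%. The chance of at least one in the gabapentin arm is 1 − (1 − q)^30:

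- q = 0.1%: 1 − 0.999^30 = 3.0%
- q = 1%: 1 − 0.99^30 = 26%

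**5. Could lactose distort the placebo adverse-event rate?** Fill weight, frequency of intolerance, chance of symptoms and the filler of the active capsule are all unstated. Assumed ranges:

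- Lactose: 100 to 500 mg per capsule gives 12 × 0.1 = 1.2 g to 12 × 0.5 = 6.0 g a day.
- Rise in the placebo rate = (share intolerant) × (chance of symptoms) × (1 − base rate).
- Low end: 0.05 × 0.10 × (1 − 0.40) = 0.3 points. High end: 0.30 × 0.50 × (1 − 0.20) = 12 points.
- 95% half-width of one arm's rate, 1.96 × √(p(1 − p)/n): 14 points at p = 0.20 and n = 30; 21 points at p = 0.40 and n = 20.

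Even the high end is smaller than the sampling error of a single arm. The rise would be a difference between arms only if the active capsule contains no lactose, or less of it.

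**The case against.** The strongest reply is that the ScreeningSurvey is listed but its content is not shown, and the consent pages are not part of the reviewed text. Section 2.e says that risks are listed in the consent form and described orally. Staff may ask about past reactions, or an affected person may decline on hearing the drug's name. This stands as a caution about how often the gap would matter. It does not close the gap, because an informal question is not a protocol criterion.

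Four stronger readings are tempting, and the documents do not support them.

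- *Lactose reactions mask gabapentin's adverse effects.* This needs four unstated quantities and largely vanishes if both capsules contain lactose. The aim in section C2 is descriptive, and section G3 plans no between-arm test of adverse events.
- *The placebo is called inert in one place and lactose in another, so the plan contradicts itself.* The sentence in section F2, "In this study, we plan to use an inert placebo and not an active drug", goes on to rule out a placebo that mimics gabapentin's side effects. It describes the type of placebo and says nothing about tolerance of lactose.
- *The omission causes one-sided loss of the primary CGI-I.* No figure supports this. Lactose symptoms would act in the placebo arm and reactions to gabapentin in the active arm, so even the direction is unclear.
- *People with past intolerance of gabapentin should also be excluded.* This is a trade-off. The design titrates each participant to the highest dose tolerated, with step-down in both arms. Excluding these people would select a more tolerant sample and could understate adverse effects.

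**Conclusion.** The omission is plain from the text and needs no assumption: a person with known hypersensitivity to gabapentin or to a capsule ingredient meets every written criterion and could be sent the capsules. This is a safety gap in eligibility that is cheap to close. Its frequency is unknown; the 3% to 26% chance of at least one affected person in the gabapentin arm rests entirely on the assumed 0.1% to 1%. The point does not alter the planned 60 enrolled, the 40 evaluable, or the analysis of the primary outcome. Any effect on the placebo adverse-event rate is possible but not established; the 0.3 to 12 points are illustrative only.

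**What to change.** Add one line to the exclusion criteria, with a matching question in the ScreeningSurvey: *known hypersensitivity to gabapentin or to any ingredient of the active or placebo capsule (including milk allergy or known lactose intolerance if lactose is the filler)*. State the composition of both capsules, including whether the active capsule contains lactose, so that the criterion can be applied and the adverse-event description can be read correctly. The cost is a short amendment, one or two screening questions and a few more screen failures.
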